12. PROCEDURE FOR HANDLING PRODUCT QUALITY COMPLAINTS

A Product Quality Complaint (PQC) refers to any written, electronic, or oral communication that alleges deficiencies related to the identity, quality, durability, reliability, safety, effectiveness or performance of test articles after they have been released for clinical trial use.

Potential complaints may come from a variety of sources including but not limited to subjects, clinical research associates (CRA), clinical operations managers (COM), medical monitors, and site personnel, etc. The following are not considered product quality complaints:

- Subject satisfaction inquiries reported via "Subjective Questionnaires" and "Patient Reported Outcomes (PRO)."
- Clinical test articles that are stored improperly or damaged after receipt at the investigational site.
- Lens replacements that occur due to drops/fall-outs.
- Damage deemed by clinicians or clinical staff to be caused by handling by the user, and not indicative of a quality deficiency (i.e. tears, rips, etc.), only in situations where there is no deficiency alleged by the subject.

Within 24 hours of site personnel becoming aware that a PQC has occurred, the PQC must be recorded in the EDC system, which will trigger an automatic email notification to the appropriate COM/CRA and Clinical QA representative. In cases where the EDC system in use is not configured to send automatic notifications or when an EDC system is not used, the COM/CRA is responsible for notifying Clinical QA upon discovery that a PQC has occurred.

Upon receipt of the EDC notification, the COM/CRA will contact the study site to collect additional information which will include:

- Date the complaint was received/recorded in the EDC System (Date of Sponsor Awareness).
- Who received the complaint.
- Study number.
- Clinical site information (contact name, site ID, telephone number).
- Lot number(s).
- Unique Subject Identifier(s).
- Indication of who first observed complaint (site personnel or subject).
- OD/OS indication, along with whether the lens was inserted.
- Any related AE number if applicable.
- Detailed complaint description (scheduled/unscheduled visit, wear time, symptoms, resolution of symptoms, etc.).
- Eve Care Provider objective (slit lamp) findings if applicable.

• Confirmation of product availability for return (and tracking information, if available), or rationale if product is not available for return

Once a complaint is received, it will be assessed by the COM, CRA, or trained site personnel to determine if it is an Adverse Event/Serious Adverse Event (AE/SAE). If the complaint results in an AE/SAE, the COM/CRA, or trained site personnel will follow Section 13 of this protocol. If the AE/SAE was potentially the result of a product quality related deficiency, these procedures also applies and will be executed in parallel.

In some cases, a PQC form may be generated in EDC by the site in error. In this event, the PQC forms will be marked "Intentionally Left Blank" or "ILB". Justification for ILB must be documented.

13. ADVERSE EVENTS

13.1. Definitions and Classifications

Adverse Event (AE) – An AE is "any untoward medical occurrence, unintended disease or injury, or untoward clinical signs (including abnormal laboratory findings) in subjects, users or other persons, whether or not related to the investigational medical device."

Note: This definition includes events related to the investigational medical device or the comparator, and to the procedures involved. For users or other persons, this definition is restricted to events related to investigational medical devices.¹

An AE includes any condition (including a pre-existing condition) that:

- 1. Was not present prior to the study, but appeared or reappeared following initiation of the study.
- 2. Was present prior to the study but worsened during the study. This would include any condition resulting from concomitant illnesses, reactions to concomitant medications, or progression of disease states.

Note: Pregnancy must be documented as an adverse event and must be reported to the clinical monitor and to the Sponsor immediately upon learning of the event.

Serious Adverse Event (SAE) – An SAE is any adverse event that led to any of the following:

- Death
- Serious deterioration in the health of the subject that resulted in any of the following:
- Life-threatening illness or injury
- Permanent or persistent impairment of a body structure or a body function
- Hospitalization or prolongation of patient hospitalization
- Medical or surgical intervention to prevent life-threatening illness or injury or permanent impairment to a body structure or a body function.
- Chronic disease
- Foetal distress, foetal death or a congenital physical or mental impairment of birth defect.

Diagnoses and conditions that are considered Ocular Serious Adverse Events include, but not limited to:

- Microbial Keratitis (MK)
- Iritis (including cells in the anterior chamber)
- Permanent decrease in best spectacle corrected visual acuity equivalent to 2 acuity lines or greater
- Central Corneal Opacity
- Central Corneal Neovascularization
- Uveitis
- Endophthalmitis
- Hypopyon
- Hyphemia
- Penetration of Bowman's Membrane
- Persistent Epithelial Defect
- Limbal cell Damage leading to Conjunctivalization

Significant Adverse Events – are defined as events that are symptomatic and warrant discontinuation (temporary or permanent) of the contact lens wear

Diagnoses and conditions that are considered Ocular Significant Adverse Events include, but not limited to the following:

- Contact Lens Induced Peripheral Ulcer (CLPU)
- Significant Infiltrative Events (SIE)
- Superior Epithelial Arcuate Lesions (SEALs)
- Any Temporary Loss of > 2 Lines of BSCVA
- Other grade 3 or higher corneal findings, such as abrasions or edema
- Non-contact lens related corneal events e.g. Epidemic Keratoconjunctivitis (EKC)
- Asymptomatic Corneal Scar
- Any corneal event which necessitates temporary lens discontinuation > 2 weeks

Non-Significant Adverse Events – are defined as those events that are usually asymptomatic and usually do not warrant discontinuation of contact lens wear but may cause a reduction in wear time. However, the Investigator may choose to prescribe treatment as a precautionary measure.

Diagnoses and conditions that are considered Ocular Non-Significant Adverse Events include, but not limited to the following:

- Non-significant Infiltrative Event (NSIE)
- Contact Lens Papillary Conjunctivitis (CLPC)
- Superficial Punctate Keratitis (SPK)
- Conjunctivitis: Bacterial, Viral, Allergic
- Blepharitis
- Meibomianitis
- Contact Dermatitis

- Localized Allergic Reactions
- Any corneal event not explicitly defined as serious or significant adverse event, which necessitates temporary lens discontinuation < 2 weeks

Adverse Device Effect (ADE) – An ADE is an "adverse event related to the use of an investigational medical device."

Note 1: This definition includes adverse events resulting from insufficient or inadequate instructions for use, deployment, implantation, installation, or operation, or any malfunction of the investigational medical device.

Note 2: This definition includes any event resulting from use error or from intentional misuse of the investigational medical device.¹

Unanticipated Adverse Device Effect (UADE) – A UADE is any serious adverse effect on health or safety or any life-threatening problem or death caused by, or associated with, the test article, if that effect, problem, or death was not previously identified in nature, severity, or degree of incidence in the investigational plan, Investigator's Brochure or protocol, or any other unanticipated serious problem associated with the test article that relates to the rights, safety and welfare of subjects.

13.2. Assessing Adverse Events

In conjunction with the medical monitor, the Investigator will evaluate adverse events to ensure the events are categorized correctly. Elements of categorization will include:

- Seriousness/Classifications (see definition in section 13.1).
- Causality or Relatedness i.e. the relationship between the test article, study treatment or study procedures and the adverse event (not related, unlikely related, possibly related, or related see definition in Section 13.2.1).
- Adverse Event Severity Adverse event severity is used to assess the degree of intensity of the adverse event (mild, moderate, or severe see definition in Section 13.2.2).
- Outcome not recovered or not resolved, recovering or resolving, recovered or resolved with sequelae, recovered or resolved, death related to adverse event, or unknown.
- Actions Taken none, temporarily discontinued, permanently discontinued, or other.

13.2.1. Causality Assessment

Causality Assessment – A determination of the relationship between an adverse event and the test article. The test article relationship for each adverse event should be determined by the investigator using these explanations:

- Not Related- An adverse event that is not related to the use of the test article, study treatment or study procedures.
- Unlikely Related An adverse event for which an alternative explanation is more likely, e.g. concomitant treatment, concomitant disease(s), or the relationship of time suggests that a causal relationship is not likely.

- Possibly Related An adverse event that might be due to the use of the test article, or to the study treatment or study procedures. An alternative explanation, e.g. concomitant treatment, concomitant disease(s), is inconclusive. The relationship in time is reasonable. Therefore, the causal relationship cannot be excluded.
- Related An adverse event that is listed as a possible adverse effect (device) or adverse reaction (drug) and cannot be reasonably explained by an alternative explanation, e.g. concomitant treatment of concomitant disease(s). The relationship in time is very suggestive, e.g. it is confirmed by de-challenge and re-challenge.

13.2.2. Severity Assessment

Severity Assessment – A qualitative assessment of the degree of intensity of an adverse event as determined by the Investigator or reported to him/her by the subject. The assessment of severity is made irrespective of test article, study treatment or study procedure relationship or seriousness of the event and should be evaluated according to the following scale:

- Mild Event is noticeable to the subject but is easily tolerated and does not interfere with the subject's daily activities.
- Moderate Event is bothersome, possible requiring additional therapy, and may interfere with the subject's daily activities.
- Severe Event is intolerable, necessitates additional therapy or alteration of therapy and interferes with the subject's daily activities.

13.3. Documentation and Follow-Up of Adverse Events

The recording and documenting of adverse events (ocular and non-ocular) begin when the subjects are exposed to the test article, study treatment or study procedure. Adverse events reported before the use of test article, start of study treatment, or study procedures will be recorded as medical history. However, if the condition deteriorates at any time during the study it will be recorded and reported as an AE. Untoward medical events reported after the subject's exit from the study will be recorded as adverse events at the discretion of the Investigator.

Upon finding an adverse event, the Principal Investigator will document the condition in the subject record and in the eCRFs and complete the Adverse Event eCRF.

Complete descriptions of all adverse events must be available in the subject record. All Adverse Events including local and systemic reactions not meeting the criteria for "serious adverse events" shall be captured on the appropriate case report form or electronic data system. All adverse events occurring while the subject is enrolled in the study must be documented appropriately regardless of relationship.

It is the Investigator's responsibility to maintain documentation of each reported adverse event. All adverse events will be followed in accordance with applicable licensing requirements. Such documentation will include the following:

- Adverse event (diagnosis not symptom).
- Drawings or photographs (where appropriate) that detail the finding (e.g., size, location, and depth, etc.).

- Date the clinical site was notified.
- Date and time of onset.
- Date and time of resolution.
- Adverse event classification, severity, and relationship to test articles, as applicable.
- Treatment regimen instituted (where appropriate), including concomitant medications prescribed, in accordance with applicable licensing requirements.
- Any referral to another health care provider if needed.
- Outcome, ocular damage (if any).
- Likely etiology.
- Best corrected visual acuity at the discovery of the event and upon conclusion of the event, if the AE is related to the visual system.

Upon discovery of an AE that is deemed 'possibly related' or 'related' to the test article or study procedures (whether related to the visual system or not), an AE review form must be completed. Additional dated and initialed entries should be made at follow-up evaluations. Separate forms must be completed for each eye if the AE is bilateral.

In addition, if an infiltrate(s) is present, he/she will complete the Corneal Infiltrate Assessment eCRF. Where necessary, a culture of the corneal lesion will be collected to determine if the infection is microbial in nature. If cultures are collected, the date of culture collection and laboratory utilized will be recorded.

Changes in the severity of an AE shall be documented to allow an assessment of the duration of the event at each level of intensity to be performed. Adverse events characterized as intermittent require documentation of the onset and duration of each episode. Changes in the assessment of relationship to the Test Article shall also be clearly documented.

Subjects who present with an adverse event shall be followed by the Investigator, within licensure, until all signs and symptoms have returned to pre-treatment status, stabilized, or been satisfactorily resolved. If further treatment beyond licensure is required, the patient will be referred to the appropriate health care provider. The Investigator will use his/her clinical judgment as to whether a subject reporting with an adverse event will continue in the study. If a subject is discontinued from the study, it will be the responsibility of the Investigator to record the reason for discontinuation. The Investigator will also document the adverse event appropriately and complete the Adverse Event eCRF. Any subjects with ongoing adverse events related to the test article, study treatment or study procedures, as of the final study visit date, should be followed to resolution of the adverse event or until referral to an appropriate health care provider, as recommended by the Investigator. Non-ocular adverse events that are not related to the test article, study treatment, or study procedures may be recorded as "ongoing" without further follow-up.

13.4. Reporting Adverse Events

The Investigator will notify the Sponsor of an adverse event by e-mail, facsimile, or telephone as soon as possible and no later than 24 hours from discovery for any serious /significant adverse events, and 2 days from discovery for any non-significant adverse event. In addition,

a written report will be submitted by the Principal Investigator to the IEC/IRB according to their requirements (Section 13.4.2). The report will comment whether the adverse event was considered to be related to the test article, study treatment or study procedures.

13.4.1. Reporting Adverse Events to Sponsor

Serious/Significant Adverse Events

The Investigator will inform the sponsor of all serious/significant adverse events occurring during the study period as soon as possible by e-mail or telephone, but no later than 24 hours following discovery of the event. The Investigator is obligated to pursue and obtain information requested by the Sponsor in addition to that information reported on the eCRF. All subjects experiencing a serious/significant adverse event must be followed up and all outcomes must be reported.

When medically necessary, the Investigator may break the randomization code to determine the identity of the treatment that the subject received. The Sponsor and study monitor should be notified prior to unmasking the test articles.

In the event of a serious/significant adverse event, the Investigator must:

- Notify the Sponsor immediately.
- Obtain and maintain in the subject's records all pertinent medical information and medical judgment for colleagues who assisted in the treatment and follow-up of the subject.
- Provide the Sponsor with a complete case history which includes a statement as to whether the event was or was not related to the use of the test article.
- Notify the IEC/IRB as required by the IEC/IRB reporting procedure according to national regulations.

Unanticipated (Serious) Adverse Device Effect (UADE)

In the event of an Unanticipated (Serious) Adverse Device Effect (UADE), the Investigator will submit a report of the UADE to the Sponsor and IEC/IRB as soon as possible, but no later than 24 hours after the Investigator first learns of the effect. This report is in addition to the immediate notification mentioned above.

The Sponsor must conduct an evaluation of the UADE and must report the results of the evaluation to FDA, the IEC/IRB and participating Investigators within 10 working days after the Sponsor first receives notification of the effect.

Non-Serious Adverse Events

All non-serious adverse events, including non-serious adverse device effects, will be reported to the sponsor by the Investigator no later than 2 days from discovery.

13.4.2. Reporting Adverse Events to the Responsible IEC/IRB and Health Authorities

Adverse events that meet the IEC/IRB requirements for reporting must be reported within the IEC/IRB's written guidelines. Each clinical site will refer to and follow any guidelines set forth

by their Approving IEC/IRB. Each clinical site will refer to and follow any guidelines set forth by their local governing Health Authorities.

The Sponsor will report applicable Adverse Events to the local health authorities according the written guidelines, including reporting timelines.

13.5. Event of Special Interest

None

13.6. Reporting of Pregnancy

Subjects reporting pregnancy (by self-report) during the study will be discontinued after the event is recorded as an Adverse Event. Once discontinued, pregnant participants and their fetuses will not be monitored for study related purposes. Pregnant participants are not discontinued from contact lens or solution related studies for safety concerns, but due to general concerns relating to pregnancy and contact lens use. Specifically, pregnant women are discontinued due to fluctuations in refractive error and/or visual acuity that occur secondary to systemic hormonal changes, and not due to unforeseen health risks to the mother or fetus.

14. STATISTICAL METHODS

14.1. General Considerations

Statistical Analysis will be undertaken by the sponsor or under the authority of the sponsor. A general description of the statistical methods to be implemented in this clinical trial is outlined below.

All data summaries and statistical analyses will be performed using the Statistical Analysis System (SAS) software Version 9.4 or higher (SAS Institute, Cary, NC).⁸ Throughout the analysis of data, the results for each subject/eye will be used when available for summarization and statistical analysis. Unscheduled visits will be summarized separately and will be excluded from the statistical analysis.

Summary tables (descriptive statistics and/or frequency tables) will be provided for all baseline variables, efficacy variables and safety variables as appropriate. Continuous variables will be summarized with descriptive statistics (n, mean, standard deviation [SD], median, minimum and maximum). Frequency count and percentage of subjects or eyes within each category will be provided for categorical data.

14.2. Sample Size Justification

This study was designed and powered to demonstrate that the binocular high luminance high contrast, visual performance (logMAR) of the Test lens at distance (4 meters), intermediate (64 cm) and near (40 cm) after 2-week of lens wear in the optimized lenses is superior to 0.00, +0.17 and +0.17 logMAR, respectively. Additionally, this study was also powered to show that CLUE vision scores for the Test lens for the hyperopic population is greater than 32 points and greater than 40 points for the myopic population. The sample size calculation included

two historical studies, and Previous hyperopic data was not available for the Test lens, therefore, data from was used because it evaluated lenses with a similar lens design on a hyperopic population. Data from was used for the myopic population since this study evaluated lenses with the same lens design and similar material as the current Test lens on a population of myopic subjects.

Table 6: Historical Binocular High Luminance High Contrast Visual Performance – 2-Week Follow-up

Chart Position	Mean	SD*	Minimum	Maximum
Distance (4 M)	-0.048	0.0943	-0.220	0.280
Intermediate (64 cm)	-0.015	0.1183	-0.240	0.320
Near (40 cm)	0.097	0.1318	-0.200	0.500

^{*}SD: Standard Deviation

Table 7: Historical CLUE Scores – 2-Week Follow-up

CLUE Domain	Strata	Baseline	2-Week Follow-up
		Mean (SD*)	Mean (SD*)
Vision	Hyperope	45.5(14.71)	47.3(18.65)
	Myope	42.9(15.43)	55.1(20.73)
Comfort	Hyperope	50.7(19.70)	60.9(22.38)
	Myope	54.5(20.39)	62.7(21.95)
Handling	Hyperope	50.9(17.26)	56.6(21.12)
	Myope	56.9(16.49)	70.6(18.02)

^{*}SD: Standard Deviation

Sample size calculations for each primary endpoint were carried out using a 2-sided one sample mean t-test, with a family wise error rate of 5%. The calculation was performed using the POWER¹¹ procedure in SAS Version 9.4⁸. The Bonferroni¹² method was used to adjust the type I error for multiple primary hypotheses $\alpha = \frac{0.05}{5} = 0.01$. A power analysis was also performed for each secondary hypothesis to test for non-inferiority of the 2-week follow-up relative to the baseline assessment with respect to CLUE vision, comfort and handling scores. The power analysis was performed for each secondary hypothesis separately using the POWER procedure and 2-sided t-test for paired means with alpha=0.05. The power Analysis was performed for different scenarios of intraclass correlation and effect sizes. The sample size required for all primary endpoints is displayed in Table 8, while the power analysis for the secondary endpoints is located in Table 9.

^{**}This summary included data from both

Table 8: Sample Size Estimates for Primary Endpoints

Endpoint	Power	Sample Size
Visual Acuity - Distance (4 M)	80.6%	42
Visual Acuity - Intermediate (64 cm)	80.1%	7
Visual Acuity - Near (40 cm)	80.7%	36
CLUE Vision Scores – Hyperopes	80.1%	18
CLUE Vision Scores – Myopes	80.9%	22

Table 9: Power Analysis for Secondary Endpoints

Endpoint	Strata	correlation	Effect size	Power
Vision – CFB*	Hyperope N=35	0.3	1	42.3%
			3	75.0%
		0.5	1	65.5%
			3	86.0%
	Myope N=45	0.3	3	78.1%
			5	91.7%
		0.5	3	88.2%
			5	97.1%
Comfort – CFB*	Hyperope N=35	0.3	3	58.4%
			5	75.0%
		0.5	3	70.8%
			5	86.3%
	Myope N=45	0.3	3	67.8%
			5	83.9%
		0.5	3	80.1%
			5	92.9%
Handling – CFB*	Hyperope N=35	0.3	3	64.8%
			5	81.2%
		0.5	3	76.9%
			5	90.8%
	Myope N=45	0.3	3	82.6%
			5	94.3%
		0.5	3	92.0%
			5	98.5%

^{*}CFB = Change from baseline (calculated as 2-week follow-up minus baseline)

Represents conservative power estimate based on the most conservative effect size and intraclass correlation.

While only 42 subjects are required to complete the study based on the sample size calculation, the plan is to compare the data from this study to another study which is similar in design and sample size and is assessing a marketed multifocal toric lens. Therefore, the sample size was increased in order to perform a meta-analysis at a later date. Moreover, as shown in Table 9, a

target completion of 80 subjects demonstrates a reasonable statistical power for the secondary endpoints under most of the assessed scenarios.

The plan is to enroll 90 eligible subjects with a target completion of 80 subjects (45 myopes and 35 hyperopes). During the enrollment period, the subject drop-out rate will be closely monitored, if an unexpectedly high dropout rate is observed, then the targeted total enrollment number maybe be increased accordingly to ensure that the target numbers of 45 myopes and 35 hyperopes subjects complete the study.

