14.4. Level of Statistical Significance

All planned primary analyses for this study will be conducted with a 2-sided type I family wise error rate of 5%. The Bonferroni¹² method will be used to adjust for the number of primary hypotheses tested. Secondary hypotheses will be tested separately with a 2-sided type I error rate of 5% individually.

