14.5. Primary Analysis

CLUE Vision Scores

Vision scores after approximately 2-weeks in the optimized lenses will be analyzed using a linear mixed model. Baseline vision scores, event (visit 1: baseline, visit 2: 1-wk non-optimized, visit 3: 1-wk optimized and visit 4: 2-wk optimized), strata (hyperope and myope) and the interaction between event and strata will be included in the model as fixed effects. Other covariates such as age, gender and add power may be included when appropriate. Site will be included as a random effect (G-side). Residual errors between measurements within the same subject across event will be model using one of the following:

- Unstructured (UN)
- Compound Symmetric (CS)

• Heterogenous Compound Symmetric (CSH)

The structure that returns the lowest corrected Akaike's Information Criterion (Keselman et al. 1998)¹³ will be selected as the structure that best fits the data. The Kenward and Roger method will be used for the calculation of the denominator of degrees of freedom.¹⁴

Primary hypothesis 1:

The null and alternative hypothesis for CLUE vision to test for superiority of the Test lens relative to the pre-defined threshold of 40 for myopes is as follows:

$$H_o$$
: $\mu_{Test} \le 40$
 H_A : $\mu_{Test} > 40$

Superiority will be declared if the lower limit of the 95% confidence interval of the adjusted mean for the Test lens is greater than 40. i.e. $P(\mu_{Test} > 40) \ge 0.975$.

Primary hypothesis 2:

The null and alternative hypothesis for CLUE vision to test for superiority of the Test lens relative to the pre-defined threshold of 32 hyperopes is as follows:

$$H_o$$
: $\mu_{Test} \le 32$
 H_A : $\mu_{Test} > 32$

Superiority will be declared if the lower limit of the 95% confidence interval of the adjusted mean for the Test lens is greater than 32. i.e. $P(\mu_{Test} > 32) \ge 0.975$.

LogMAR Visual Acuity

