14.6. Secondary Analysis

CLUE Vision, Comfort and Handling Scores

Vision, Comfort and Handling scores after approximately 2-weeks in the optimized lenses will be analyzed separately using a linear mixed model. event (visit 1: baseline, visit 2: 1-wk non-optimized, visit 3: 1-wk optimized and visit 4: 2-wk optimized), strata (hyperope and myope) and the interaction between event and strata will be included in the model as fixed effects. Other covariates such as age, gender and add power may be included when appropriate. Site will be included as a random effect (G-side). Residual errors between measurements within the same subject across event will be model using one of the following:

- Unstructured (UN)
- Compound Symmetric (CS)
- Heterogenous Compound Symmetric (CSH)
- Spatial Power (SP(POW))

The structure that returns the lowest corrected Akaike's Information Criterion (Keselman et al. 1998)¹³ will be selected as the structure that best fits the data. The Kenward and Roger method will be used for the calculation of the denominator of degrees of freedom.¹⁴

Hypothesis Testing

The null and alternative hypotheses for non-inferiority are as follows and will be conducted separately for each strata (hyperopes and myopes) and CLUE vision, comfort and handling:

$$H_0$$
: $\Delta \le -5$
 H_0 : $\Delta > -5$

Where Δ is the change from baseline to 2-week follow-up (2-week follow up minus baseline). Non-inferiority of the 2-week follow-up CLUE score relative to the baseline CLUE scores of subjects' habitual lens was concluded if the lower limit of the 95% CI was above -5 (Pr: 2 – wk minus baseline > -5,) > 0.975.

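### Section 14.2 says 2-sided tests, but Table 8 reproduces only at one-sided 0.01 and Table 9 (23 of 24 cells) only at one-sided 0.05, so secondary power is overstated by about 2 to 13 points

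*Combined protocol and SAP*

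**What the plan says.** On the primary endpoints, Section 14.2 says: "Sample size calculations for each primary endpoint were carried out using a 2-sided one sample mean t-test". It applies Bonferroni, giving 0.05/5 = 0.01 per hypothesis. On the secondary endpoints, the power analysis was "performed for each secondary hypothesis separately using the POWER procedure and 2-sided t-test for paired means with alpha=0.05".

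Two conclusions rest on the resulting tables. From Table 8: "While only 42 subjects are required to complete the study based on the sample size calculation". From Table 9: a "target completion of 80 subjects demonstrates a reasonable statistical power for the secondary endpoints under most of the assessed scenarios".

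The analysis sections set the levels at which the tests will be judged:

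- Section 14.4 gives a 2-sided 5% family-wise rate for the primaries and says the Bonferroni "method will be used to adjust for the number of primary hypotheses tested". For the secondaries: "Secondary hypotheses will be tested separately with a 2-sided type I error rate of 5% individually".
- Section 14.5 declares success on unadjusted 95% intervals. For myopes, for example, the requirement is that the "lower limit of the 95% confidence interval of the adjusted mean for the Test lens is greater than 40".
- Section 14.6 says non-inferiority "was concluded if the lower limit of the 95% CI was above -5".

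**The concern.** The printed tables look too favourable for the tests that Section 14.2 names. If they were run one-sided at the full nominal alpha, they match neither the stated method nor the decision rules. A lower 95% limit is a one-sided 0.025 test, not a one-sided 0.05 test.

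For the primaries, the number said to be required would be wrong, but the planned numbers are far larger. For the secondaries, Table 9 is the only evidence offered for adequate power. If it is inflated, a failed non-inferiority test could be read as evidence against the lens when the test had a substantial chance of failing anyway. Hyperope vision is the exposed case: Table 7 shows a historical change of only 47.3 − 45.5 = +1.8 points.

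**Working it through.** **Inputs.** Means and SDs are from Tables 6 and 7. Thresholds are from Section 2.3: 0.00, +0.17 and +0.17 logMAR; CLUE vision 32 for hyperopes and 40 for myopes; non-inferiority margin −5. Completers are 45 myopes and 35 hyperopes. Acuity is tested on all 80, since hypotheses 3 to 5 are not split by stratum.

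**Method.** Exact noncentral t with n − 1 degrees of freedom and noncentrality (shift/SD) × √n. For the primaries, shift = |historical mean − threshold|. For the secondaries, shift = effect + 5 and SD of change = √(s₁² + s₂² − 2ρs₁s₂).

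**Table 8.** Worked case, distance acuity: 0.048/0.0943 = 0.509, and 0.509 × √42 = 3.30. Power at n = 42 is 80.6% at one-sided 0.01, which is the printed value. It is 72.2% at 2-sided 0.01 and 89.6% under a 95% interval.

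| Endpoint | Shift/SD | Printed N (power) | One-sided 0.01: N (power) | 2-sided 0.01: N needed; power at printed N | 95% CI rule: N needed; power at printed N |
|---|---|---|---|---|---|
| Distance | 0.048/0.0943 | 42 (80.6%) | 42 (80.6%) | 49; 72.2% | 33; 89.6% |
| Intermediate | 0.185/0.1183 | 7 (80.1%) | 7 (80.1%) | 9; 66.2% | 6; 92.8% |
| Near | 0.073/0.1318 | 36 (80.7%) | 36 (80.7%) | 42; 72.2% | 28; 89.8% |
| CLUE, hyperopes | 15.3/18.65 | 18 (80.1%) | 18 (80.8%) | 21; 71.3% | 14; 90.6% |
| CLUE, myopes | 15.1/20.73 | 22 (80.9%) | 22 (80.7%) | 26; 71.5% | 17; 90.3% |

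All five Ns match one-sided 0.01 and none matches the stated test. The myope power is within what rounding of Table 7 allows (80.4 to 81.0%). The hyperope 80.1% is just outside its range (80.5 to 81.1%), a small slip that leaves N = 18 unchanged.

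**Primary power at 80/80/80/35/45 completers**, 2-sided 0.01, in the order of the table: 97.0, about 100, 98.8, 97.9 and 98.3%. Under 95% intervals each is at least 99.4%. For all five together, the product assuming independence is 92.3% at 2-sided 0.01 and 98.7% under 95% intervals. Simulation allowing correlation between acuity positions gave 92.5 to 93.4% and 98.7 to 99.0%.

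**Table 9.** Worked case, hyperope vision at ρ = 0.3: SD of change = √(14.71² + 18.65² − 2 × 0.3 × 14.71 × 18.65) = 19.99. At effect 3 the shift is 8 and n = 35. Power is 75.0% at one-sided 0.05, as printed, and 63.3% at 2-sided 0.05. The 2-sided column below is, in effect, the Section 14.6 rule.

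| Domain, stratum | ρ | Effect | Printed | One-sided 0.05 | 2-sided 0.05 |
|---|---|---|---|---|---|
| Vision, hyperope | 0.3 | 1 | 42.3 | 53.8 | 40.7 |
| | 0.3 | 3 | 75.0 | 75.0 | 63.3 |
| | 0.5 | 1 | 65.5 | 65.5 | 52.6 |
| | 0.5 | 3 | 86.0 | 86.0 | 77.1 |
| Vision, myope | 0.3 | 3 | 78.1 | 78.1 | 67.2 |
| | 0.3 | 5 | 91.7 | 91.7 | 85.3 |
| | 0.5 | 3 | 88.2 | 88.2 | 80.3 |
| | 0.5 | 5 | 97.1 | 97.1 | 94.0 |
| Comfort, hyperope | 0.3 | 3 | 58.4 | 58.4 | 45.3 |
| | 0.3 | 5 | 75.0 | 75.0 | 63.3 |
| | 0.5 | 3 | 70.8 | 70.8 | 58.4 |
| | 0.5 | 5 | 86.3 | 86.3 | 77.5 |
| Comfort, myope | 0.3 | 3 | 67.8 | 67.8 | 55.3 |
| | 0.3 | 5 | 83.9 | 83.9 | 74.4 |
| | 0.5 | 3 | 80.1 | 80.1 | 69.6 |
| | 0.5 | 5 | 92.9 | 92.9 | 87.1 |
| Handling, hyperope | 0.3 | 3 | 64.8 | 64.8 | 51.9 |
| | 0.3 | 5 | 81.2 | 81.2 | 70.8 |
| | 0.5 | 3 | 76.9 | 76.9 | 65.6 |
| | 0.5 | 5 | 90.8 | 90.8 | 83.9 |
| Handling, myope | 0.3 | 3 | 82.6 | 82.6 | 72.8 |
| | 0.3 | 5 | 94.3 | 94.3 | 89.4 |
| | 0.5 | 3 | 92.0 | 92.0 | 85.8 |
| | 0.5 | 5 | 98.5 | 98.5 | 96.6 |

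In 23 cells the printed value equals the one-sided 0.05 value and exceeds the 2-sided value by 1.9 to 13.1 points. The exception is the first row. Its 42.3% is what one-sided 0.05 gives at effect 0, where 2-sided power is 30.1%. That suggests a wrong label or value, but the document does not settle which.

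Cells at or above 80% fall from 14 to 8 of 24; 13 of 24 reach 70%. At the Table 7 mean changes with ρ of 0.3 to 0.5, 2-sided power is 50 to 63% for hyperope vision, 76 to 88% for hyperope handling, and at least 93% for the other four.

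**The case against.** The best defence is that little depends on these tables. Section 14.2 says N was raised above 42 for a later comparison with another study, and Table 9 is added only as support. Under Section 2.3 the study objective depends on the primary hypotheses alone, and the secondaries gate nothing. All of that is right, and it limits the point to a correction of stated figures.

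It can also be said that the hypotheses are directional, so the label 2-sided may be the mistake rather than the numbers. That could explain Table 8, but one-sided 0.01 would then conflict with the 2-sided 5% family-wise rate in Section 14.4 and with the intervals in Section 14.5. It cannot rescue Table 9, because Section 14.6 fixes a one-sided 0.025 test.

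Three further points stand in part. Table 9 already prints three of its four hyperope vision cells below 80%, so the weakness is visible and only its size is understated. The plan sets no cut-off for reasonable power, and just over half the cells still reach 70%. The paired t-test only approximates the four-visit mixed model, and the correlation is unknown: at ρ = 0.6 and effect 3, outside the plan's grid, hyperope vision power would be 85.1%.

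**Conclusion.** The concern holds. Both tables were evidently computed one-sided at the full nominal alpha, contrary to Section 14.2, and neither matches the rules in Sections 14.5 and 14.6. Table 9 overstates secondary power by about 2 to 13 points. No hyperope vision scenario in the plan's own grid reaches 80%. The figure of 42 is too low for the stated 2-sided 0.01 test (49) and too high for the 95% interval rule (33).

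Enrolment and the primary conclusions are not affected: power per primary test is at least 97.0% at the planned completers on either rule.

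These results rest on the historical means and SDs in Tables 6 and 7, on pooling all 80 completers for acuity, and on ignoring site and covariates, as the plan's calculation also does. The joint-power figures also assume CLUE scores are independent of acuity.

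**What to change.** 1. Reconcile the primary alpha across Sections 14.2, 14.4 and 14.5, then recompute Table 8 at that level: 33/6/28/14/17 if the 95% interval rule stands, or 49/9/42/21/26 if Bonferroni at 2-sided 0.01 stands. Section 2.3 requires every primary hypothesis to be met. If success is claimed only on that basis, type I error control does not need the alpha to be split, which bears on the choice.
2. Restate Table 9 at 2-sided 0.05, to match Section 14.6.
3. Resolve the 42.3% cell: 40.7% if effect 1 is the right label, 30.1% if the value belongs to effect 0. Check the hyperope 80.1% in Table 8.
4. Replace 42 with 33 or 49, described as 80% power per test. The two CLUE strata sum to 14 + 17 = 31 or 21 + 26 = 47, so they fit within it. Add the joint power at 45 and 35 completers: about 99% or 92 to 93%.
5. Qualify the sentence on secondary power: state the level meant by reasonable, and say that hyperope vision falls below 80% in every scenario shown.

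The cost is a re-run of the power procedure and edits to Sections 14.2, 14.4 and 14.5. Enrolment and data collection do not change. The only downside is less favourable stated secondary power.
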